6.1.4 Medical History

Medical history will be presented by the pre-specified terms, as collected in the eCRF using MedDRA Primary System Organ Class / Preferred Term. The summary of medical history data will be presented in frequency tables, showing the number of subjects with medical history findings (i.e., listed conditions of previous diagnoses, diseases, or surgeries) that started before signing of the informed consent and that are considered relevant to the study.

6.1.5 **Protocol Deviations**

Frequency tables will present a summary of protocol deviations related to inclusion and exclusion criteria, as well as important protocol deviations; these will be presented by visit and treatment. The summary will be based on SAF analysis set.

6.1.6 Prior and Concomitant Medications

The dictionary used for coding concomitant medications is the World Health Organization Drug Registration and Listing. Frequency tables displaying frequency of subjects for each drug category summarized by Anatomical Therapeutic Chemical (ATC) class and coded terms will be used to summarize the number and percentage of subjects with prior and

concomitant medications. The following definitions for prior and concomitant medications will be used:

- Prior medication: medication stopped prior to the date of randomization
- Concomitant medication in main treatment period (PA), extension period (EP), follow-up period (FP), total treatment analysis principle (TA), overall analysis principle (OA) (i.e. at least one dose was administered within the respective period)
- Concomitant medication started in main treatment period (PA), extension period (EP), follow-up period (FP), total treatment analysis principle (TA), overall analysis principle (OA) (i.e. first administration of concomitant medication occurred within the respective period)

The frequency tables of concomitant medications will be presented by treatment group and time period.

Additionally, frequency tables and listings of subjects taking prohibited concomitant medications (see study protocol section 6.5) will be provided.

6.1.7 Extent of Exposure and Compliance

All summaries related to exposure to the study intervention will be presented by treatment group based on SAF analysis set.

The treatment duration (date of last study intervention - date of first study intervention+1 day) will be summarized descriptively. Additionally, the number of subjects by treatment duration category will be given (≤ 4 weeks, $\geq 4-\leq 8$ weeks, $\geq 8-\leq 12$ weeks, $\geq 12-\leq 24$ weeks, ≥ 24 weeks).

The time on study intervention (treatment duration excluding days off study intervention) will be calculated and summarized descriptively.

Compliance will be presented by visits as entered in the eCRF and summarized based on FAS analysis set. The number of subjects with at least 80% compliance will be presented.

```
Study Drug Compliance = 100 \times \frac{\text{Total number of doses with injections given}}{\text{Total number of doses with injections expected}}
```

If a patient discontinued the study intervention, the total number of doses with injections expected is counted, per the schedule of injections, up to the last attended study visit during the total treatment period.

6.1.8 Baseline Renal Replacement Therapy

Information on the renal replacement therapy at baseline will be evaluated similar to the other baseline characteristics. In this context the use of unfractionated heparins and LMWH for dialysis maintenance at baseline will be descriptively summarized by treatment groups and overall.

6.2 Efficacy

6.2.1 Analysis of Exploratory Efficacy Variable(s)

Two exploratory efficacy variables will be considered.

First exploratory efficacy composite endpoint consisting of the following components:

• Death due to MI, ischemic stroke, pulmonary embolism (PE), non-CNS systemic embolism (SE) and undetermined - presumed cardiovascular death

- Stroke (ischemic or undetermined type)
- MI
- Major amputation of vascular etiology
- Acute limb ischemia
- Symptomatic VTE
- Systemic embolism

Second exploratory efficacy endpoint:

• Thrombosis of the arterio-venous grafts or fistulas

The frequency and percentage of participants with an exploratory efficacy event will be reported where the denominator will be total number of participants in each treatment group, within the SAF analysis set and PA data scope. The corresponding exact binomial two-sided 95% confidence interval calculated using Blaker's method will be provided.

Exposure adjusted incidence rate (100 person-years) analysis will be performed by treatment group and overall. In addition, the analysis of the exploratory efficacy variable will be conducted as a descriptive time to first event analysis separately for the three Fesomersen dose groups and placebo, similar to the primary safety analysis (i.e. only treatment emergent efficacy events which occurred during the main treatment period will be considered). Thus, the descriptive analysis focuses on estimating the efficacy under constant BAY2976217 concentration during chronic treatment. This analysis will be based on SAF analysis set and the PA data scope.

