8.1 Efficacy Assessments

The following efficacy outcomes will be assessed by the blinded CIAC in accordance with the pre-specified endpoint criteria in the adjudication charter:

- Death due to MI, stroke, PE or SE
- Non-fatal MI
- Non-fatal stroke

07 JUL 2021 Page: 42 of 90

- Major amputation of vascular etiology
- Acute limb ischemia (new onset ischemia or worsening or pre-existing ischemia)
- Venous thromboembolism
- Thrombosis of the arterio-venous grafts or fistulas

All deaths and events suspected to be related to cardiovascular disease, or other arterial or venous thrombosis events (including arterio-venous access thrombosis), but not limited to these, will be reported as an AE or SAE as per adverse event reporting procedure in Section 8.3. Additionally, the event will be triggered, within the eCRF, for adjudication by the CIAC. Details for the adjudication process are described in the adjudication charter.

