9.4.6.1 Exploratory efficacy endpoints

The exploratory efficacy endpoints, as assessed by the CIAC, are:

- Incidence of composite and event types of death due to MI, stroke, PE and SE, and non-fatal stroke, non-fatal MI, VTE, major amputation of vascular etiology, and acute limb ischemia
- Incidence of thrombosis of the arterio-venous grafts or fistulas.

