• To evaluate the effect of	Exploratory Efficacy Endpoints
Fesomersen on	• Incidence of the composite and event types of death due to MI, stroke, PE and SE, and stroke,

Table 2-1: Objectives and Endpoints

Objectives	Estimands/Endpoints
thromboembolic events as compared to placebo	 MI, VTE, major amputation of vascular etiology, and acute limb ischemia as assessed by the blinded CIAC Incidence of thrombosis of the arterio-venous
	grafts or fistulas, assessed by the blinded CIAC Other pre-specified Safety Endpoints
• To further evaluate the safety profile of Fesomersen as compared to placebo	• Incidence and severity of AESIs- hepatic enzyme elevation, thrombocytopenia
	• Changes in vital signs and, laboratory assessments
	• Incidence and severity of bleeding of the arterio-venous grafts or fistulas
• To further evaluate the	Other Pre-specified Pharmacodynamic Endpoints
pharmacodynamics of Fesomersen as compared to placebo	• Maximum change in PT, INR and aPTT during the main treatment period
P	• Extent and frequency of clotting on the dialysis filters & circuit
	Changes in d-dimer
	• Thrombin-antithrombin complex (TAT) and Prothrombin fragment 1 + 2 (F1.2)
Other pre-specified	
• To further investigate Fesomersen (e.g. mode-of- action-related effects, safety) and to further investigate pathomechanisms deemed relevant to cardiovascular and renal diseases and associated health problems	• Various biomarkers (e.g. diagnostic, safety, pharmacodynamic, monitoring, or potentially predictive biomarkers)
• To evaluate potential associations between genotypic information and clinical efficacy and / or pharmacodynamics effects	

It is important to note, based on the current expert assessment of the COVID-19 Public Health Emergency, it is to be expected that only a very limited number of patients (<5) will suffer from confirmed COVID-19. Besides, as ESRD patients have to go to the hospital regularly, no increase in missing data is to be expected. For this reason, no intercurrent event linked to the COVID-19 Public Health Emergency is accounted for this study. However, any premature discontinuation will be summarized, and selected analyses will be repeated by confirmed COVID-19 (Yes/No) as reported by the investigator.

3. Study Design

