6.5 Data affected by the war in Ukraine

Data 'affected' by the war in the Ukraine will be assessed during the final Blind Review Meeting and will be documented in the Blind Review Report. As the war started after the primary analysis was completed, it is expected that only data in the post study intervention follow-up period will be affected, the impact of the war is considered to be minor/not substantial on the statistical analysis and on interpretation on the study results. Any missingness due to the war is considered as not related to the outcomes of the study i.e. the missingness is likely noninformative. The EMA guidance "Points to consider on the impact of the war in Ukraine on methodological aspects of ongoing clinical trials" released by the Biostatistics Working Party will be taken into account.

7. Document History and Changes in the Planned Statistical Analysis

Protocol No.: BAY 2976217/21170

- Approval of the SAP version 1.0 dated 25 AUG 2020
- The following changes were made in the SAP Version 2.0 dated 15 DEC 2021:
 - Updated the data scope definitions to cover the follow up and extension periods alone.
 - Updated the concomitant medication period definitions
 - Adapted the safety and efficacy outcome variable sections with the exploratory competing risk analysis including with cause-specific and sub-distribution hazard models
 - \circ Clarified definition of the subgroup of subjects with COVID-19
 - General updates based on new version of the protocol
 - \circ $\;$ Updates to the PK/PD sections based on expert opinion and review
 - o Updated BAY 2976217 to 'Fesomersen'.
 - \circ $\,$ Removed the following subgroups as they do not make sense
 - Medical condition that likely led to RRT
 - Time since the start date for most recent Hemodialysis (including hemodiafiltration)
 - Removed text from section 6.4.3 due to repetition and referenced the text in section 6.4.1.
 - Updated the safety analysis set definition to clarify how subjects who were mis-dosed would be handled
- The following changes were made in the SAP version 3.0 dated 01 FEB 2022:
 - Added undetermined- presumed cardiovascular death to efficacy composite
 - Updated analysis periods and data scopes so they no longer depend on visits
 - Aligned the subgroups across safety and efficacy analyses
- The following changes were made in the SAP version 4.0 dated 31MAY2022:
 - Added section 6.5 relating to the handling of data affected by the war in Ukraine.

8. References

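### SAP 6.2.1 counts a different exploratory efficacy composite from Protocol 9.4.6.1 and SAP Table 2-1, and the competing-event rule in SAP 6.2.2.2 does not fit it

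*SAP*

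**What the plan says.** Protocol 9.4.6.1 defines the endpoint as "Incidence of composite and event types of death due to MI, stroke, PE and SE, and non-fatal stroke, non-fatal MI, VTE", followed by major vascular amputation and acute limb ischemia. Protocol Table 3-1 and the list of adjudicated outcomes in Protocol 8.1 have the same content. Protocol 8.1 has the outcomes assessed "in accordance with the pre-specified endpoint criteria in the adjudication charter".

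SAP Table 2-1 agrees with the protocol on stroke and on the causes of death: "Incidence of the composite and event types of death due to MI, stroke, PE and SE, and stroke", then the remaining components.

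SAP 6.2.1, which specifies what is analyzed, has a different list. Its death component is "Death due to MI, ischemic stroke, pulmonary embolism (PE), non-CNS systemic embolism (SE) and undetermined - presumed cardiovascular death". Its stroke component is "Stroke (ischemic or undetermined type"). It also lists "systemic embolism" as a component in its own right.

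The SAP document history (section 7) has one specific entry on this composite, under version 3.0: "Added undetermined- presumed cardiovascular death to efficacy composite".

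SAP 6.2.2.2 plans a competing-risk analysis of the exploratory variables. Its competing event is any death from a cause other than the four named in Table 2-1, with stroke unqualified.

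**The concern.** An endpoint table and the section that implements it should count the same events. Here they do not, so a reader who takes the definition from the protocol or Table 2-1 will misread the result produced under SAP 6.2.1.

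The second problem is operational. A competing-risk analysis needs every death placed in exactly one class. The rule in 6.2.2.2 was not re-derived when the component list changed, so some deaths fall in two classes and others in none. A programmer would have to choose, and the cumulative incidence and cause-specific results would depend on that choice.

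The endpoint is exploratory, but it has a use. Protocol 9.4 includes exploratory efficacy in the unblinded primary analysis, and Protocol 4.1 says that analysis is meant to speed Phase 3 dose selection. Protocol 2.3 describes the anticipated pivotal composite with stroke unqualified.

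**Working it through.** **Step 1. Component lists side by side.**

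| Event | Protocol 3, 8.1, 9.4.6.1 | SAP Table 2-1 | SAP 6.2.1 |
|---|---|---|---|
| Ischemic or undetermined stroke | counted (stroke unqualified) | counted | counted |
| Hemorrhagic stroke, non-fatal | counted if stroke means all types | same | not counted |
| Hemorrhagic stroke, fatal | counted if stroke means all types | same | not counted |
| Death due to systemic embolism | counted | counted | counted (non-CNS) |
| Non-fatal systemic embolism | not listed | not listed | counted |
| Undetermined, presumed CV death | not listed | not listed | counted |

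MI, deaths from MI and PE, vascular amputation and acute limb ischemia are in all three lists. VTE is also common to all three, although 6.2.1 adds the word symptomatic. Protocol 2.3 and 8.3.4 also use that word, so this is a smaller wording point to settle at the same time.

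**Step 2. Deaths under SAP 6.2.1 and 6.2.2.2 together.**

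| Death | Component in 6.2.1? | Competing event in 6.2.2.2? | Result |
|---|---|---|---|
| MI, ischemic stroke, PE, SE | yes | no | consistent |
| Undetermined, presumed CV | yes | yes (none of the four named causes) | both |
| Hemorrhagic stroke | no | no (stroke is one of the four) | neither |
| Other causes | no | yes | consistent |

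**Step 3. Traceability.** Of the three differences, only presumed CV death has a specific history entry. The version 2.0 entries are general (outcome sections adapted for competing risks; updates for the new protocol). They do not mention stroke type or systemic embolism. SAP 6.5 shows that the primary analysis was complete before version 4.0, but neither document dates that analysis.

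**Step 4. Scale.** The plan states no event rate, power or precision for this composite, so there is no figure to reproduce.

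- Group size: 72 per dose group and 3 × 24 = 72 pooled placebo (Protocol 9.2), assuming all randomized participants are dosed.
- One reclassified participant: 1/72 = 1.39 percentage points. One presumed CV death coded as an event adds this amount to the crude incidence; coded only as a competing event, it adds nothing.
- A fatal hemorrhagic stroke that is neither class might be censored by default. If it came before any other event or dropout, each later event would weigh 1/71 = 1.41 points instead of 1.39. That effect is small, but treating a dead participant as still able to have the event is wrong in principle.
- Relative size, by assumption only: Protocol 2.3 aims for a 25% relative reduction worth more than 3 points absolute, which implies a control rate of at least 3%/25% = 12%. No time base is given. If 12% accrues evenly over 1, 2 or 3 years, the expected events per group in 24 weeks are 72 × 0.12 × 24/52 = 4.0, or 2.0, or 1.3. One event is then 1/4.0 = 25% to 1/1.33 = 75% of a group's count.

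**The case against.** The strongest defense is that the 6.2.1 list is a coherent choice. It counts ischemic events as efficacy and leaves intracranial bleeding to safety. Protocol 8.2.1 classes symptomatic intracranial bleeding as major bleeding, so a hemorrhagic stroke on treatment enters the primary endpoint. A reader might infer that the narrower composite hides harm or makes the drug look better. The documents do not support that: the event is still counted under safety, one change removes events while two add them, and no rates by arm are given.

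The adjudication charter, which is not among the documents, may define stroke more narrowly than the protocol's plain word. A reader might take the protocol to promise stroke of any type, but neither 9.4.6.1 nor 2.3 says so. The hemorrhagic stroke difference therefore rests on the ordinary reading. A narrower charter definition would not explain the presumed CV death or systemic embolism differences, or the double classification.

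Protocol 9.4.6 leaves further detail on exploratory endpoints to the SAP, and presumed CV death is a declared change. Both points stand. What remains is that Table 2-1 and 6.2.2.2 were not brought into line.

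SAP 6.2.1.1 analyzes components separately, which helps to isolate the added events. It does not recover a non-fatal hemorrhagic stroke, which is not a component. Its list of deaths might be read as a second composite, but it is a breakdown of all deaths and need not match 6.2.1.

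A reader might also suspect that the unrecorded changes followed unblinding. Nothing shows this; the stroke restriction could date from SAP version 1.0.

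**Conclusion.** The point holds as an inconsistency of definition with one operational error. SAP 6.2.1 differs from Protocol 9.4.6.1 and SAP Table 2-1 in three respects: stroke type, non-fatal systemic embolism, and presumed CV death. Only the third is specifically recorded. With 6.2.2.2 as written, presumed CV deaths are classified twice and fatal hemorrhagic strokes not at all, so the competing-risk analysis cannot be programmed without an unstated decision.

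The size is 1.4 percentage points per reclassified participant at 72 per group. The share of a group's events depends on rates that the documents do not give; the 25% to 75% range is an illustration under the stated accrual assumptions. The direction is not known.

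The endpoint is exploratory, and Protocol 9.1 plans no hypothesis testing. The primary bleeding result and the sample size are unaffected. This should be corrected, but it does not threaten the trial's main conclusion.

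**What to change.** 1. Adopt one component list and use it in Protocol 3, 8.1 and 9.4.6.1, SAP Table 2-1 and SAP 6.2.1. State the stroke types, whether non-fatal systemic embolism counts, whether presumed CV death counts, and whether VTE must be symptomatic.
2. In SAP 6.2.2.2, define the competing event as any death that is not a component of that list. Each death then has exactly one class.
3. In the SAP history, record each component change with its version and its date relative to the unblinded primary analysis.
4. If the 6.2.1 list is kept as the main analysis, also report the protocol-defined composite, with stroke unqualified, as a supplementary output.
5. Leave the breakdown of all deaths in SAP 6.2.1.1 as it is.

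Which list should be the main one is the sponsor's choice. The cost is wording and, under item 4, one additional output. Protocol 8.3.10 already sends all deaths and all suspected cardiovascular, thrombotic and non-routine bleeding events to adjudication, so no new data collection is foreseen.

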9.3 Populations for Analyses

The following populations are defined:

Population	Description						
Enrolled	All participants who sign the ICF						
Full analysis set	All participants randomized who have received at least 1 dose of study intervention. Participants will be analyzed according to the intervention they were randomized.						
Safety analysis set	All participants randomly assigned to study intervention and who took at least 1 dose of study intervention. Participants will be analyzed according to the intervention they received.						
Pharmacokinetic set	All LICA-treated participants with at least 1 PK sample in accordance with the PK sampling schedule (Section 8.5) and without deviation from the protocol that would interfere with the evaluation of the PK data will be included in the PK analysis.						
Pharmacodynamic set	All participants with at least 1 PD sample in accordance with the PD sampling schedule and without deviation from the protocol that would interfere with the evaluation of the PD data will be included in the PD analysis.						
Listing only set	All participants who signed consent but are not randomized.						

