9.4.1 General considerations

9.4.1.1 Planned Methods of Analysis

Descriptive statistics will be provided by treatment group for all demographic variables, safety endpoints, and exploratory endpoints. The placebo groups from each cohort will be combined, so that there are four treatment groups to be included for analysis—40 mg, 80 mg, 120 mg, and placebo, all equal in size.

- The safety analysis set will be used for all safety endpoints, including the primary endpoint.
- The full analysis set will be used for the exploratory endpoints or otherwise specified.
- The PK analysis set will be used for the pharmacokinetic endpoints, and
- The PD analysis set will be used for the pharmacodynamics endpoints.

For categorical variables, frequencies and proportions will be provided by treatment group. For continuous variables, means, medians, standard deviations, standard error of mean, interquartile range (25th percentile, 75th percentile), and range (minimum, maximum) will be provided by treatment group. For continuous variables collected at multiple time points, the descriptive statistics will be provided at each time point.

All analyses and tabulations will be performed using SAS@ Version 9.2 or higher or if applicable, other software.

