5.1 Assignment of Analysis Sets

All subjects who have been randomized in the study are valid for assignment to analysis sets. The following populations are defined:

	F
Population	Description
Enrolled	All participants who sign the ICF
Full analysis set (FAS)	All participants randomized who have received at least 1 dose of study intervention. Participants will be analyzed according to the intervention they were randomized.
Safety analysis set (SAF)	All participants randomly assigned to study intervention and who took at least 1 dose of study intervention. Participants will be analyzed according to the intervention they received. If a participant was administered, in error, a different dose to that which they were randomized to, they will be analyzed according to the intervention received most frequently (i.e. at > 50% of visits), in cases where 2 different doses were administered for the same number of visits, the participant would be excluded from the safety analysis set.
Pharmacokinetic set (PK)	All Fesomersen-treated participants with at least 1 PK sample in accordance with the PK sampling schedule (Section 8.5.1 of the study protocol) and without deviation from the protocol that would interfere with the evaluation of the PK data will be included in the PK analysis.
Pharmacodynamic set (PD)	All participants with at least 1 PD sample in accordance with the PD sampling schedule and without deviation from the protocol that would interfere with the evaluation of the PD data will be included in the PD analysis.
Listing only set	All participants who signed consent but are not randomized.

Table 5-1: Populations

If the safety and full analysis sets are identical, i.e. all subjects received the treatment to which they were randomized, the full analysis set will not be used.

The planned analyses for the primary, secondary, exploratory, and PK-PD endpoints are summarized in but not limited to Table 5-2 below

Endpoints	Analysis Type	Analysis set	Data Scope
Primary Endpoint(s)	Main	SAF	PA ^{a)}
	Additional	SAF	TA ^{a)}
	Exploratory	SAF	OA ^{b)}
	Subgroup	SAF	PA ^{a)}
		SAF	TA ^{a)}
Secondary Endpoint(s)	Main	SAF	PA ^{a)}
	Additional	SAF	TA ^{a)}
	Exploratory	SAF	OA ^{b)}
Exploratory Endpoint(s)	Main	SAF	PA ^{a)}
	Additional	SAF	TA ^{a)}
	Exploratory	SAF	OA ^{b)}
		FAS	PA ^{b)}
		FAS	TA ^{b)}
	Subgroup	SAF	PA ^{a)}
	C .	SAF	TA ^{a)}
PK, PD Endpoint(s)			
Trough concentrations	Main	PK	OA
Maximum change in FXI	Main	PD	OA
antigen levels			

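### The SAP makes the as-treated safety set the main set for exploratory efficacy, an unrecorded departure from the protocol's as-randomised default that lets early stopping change a mis-dosed participant's arm

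*SAP*

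**What the plan says.** Protocol 9.4.1.1 allocates the analysis sets. For safety: "The safety analysis set will be used for all safety endpoints, including the primary endpoint". For the rest: "The full analysis set will be used for the exploratory endpoints or otherwise specified". Protocol 9.4.6.1 classes the thromboembolic composite and access thrombosis as exploratory efficacy endpoints and names no other set for them. For the FAS, Protocol 9.3 states: "Participants will be analyzed according to the intervention they were randomized".

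SAP 6.2.1 uses SAF with the PA data scope for the event proportions, and says of the time-to-first-event analysis: "This analysis will be based on SAF analysis set and the PA data scope". SAP Table 5-2 agrees: for exploratory endpoints the Main row is SAF/PA. FAS/PA and FAS/TA are listed as Exploratory, and SAP 6.2.2 plans them as supplementary runs. The footnotes in Table 5-2 mark the SAF/PA and SAF/TA rows as on-treatment and the FAS rows as treatment policy.

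SAP Table 5-1 defines the SAF: "Participants will be analyzed according to the intervention they received". For a participant given a wrong dose in error, "they will be analyzed according to the intervention received most frequently", with the threshold at more than half of visits. A participant with two doses given equally often leaves the set. SAP 5.1 drops the FAS only if it is identical to the SAF.

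SAP section 7 logs the mis-dosing clarification (version 2.0). It has no entry on the choice of set for efficacy.

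**The concern.** Grouping by treatment received is conventional for bleeding and adverse events. For an efficacy comparison it gives up the protection of randomisation for anyone whose received and randomised treatments differ. The SAP's rule adds a specific problem: it uses the participant's whole dosing record, and the length of that record is determined after randomisation. A thromboembolic event or a death can shorten it, so the endpoint itself can influence which arm the event is counted in, or whether it is counted at all.

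The unblinded primary analysis covers exploratory efficacy (Protocol 9.4) and is intended to speed up Phase 3 dose selection (Protocol 4.1). The choice of set also spreads: SAP 6.2.1.1 has the component and death analyses follow the main efficacy analysis, and SAP 6.2.2.3 runs the subgroups on SAF only.

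**Working it through.** **1. Arm size.** Protocol 9.2 gives 96 per cohort, 72 active and 24 placebo. Pooled placebo is 3 × 24 = 72, and 4 × 72 = 288, the stated total. One event in an arm is 1/72 = 1.39 points.

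**2. What separates the two sets.** Both require randomisation and at least one dose. They differ only in the arm assigned to mis-dosed participants and in the exclusion of ties.

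**3. The SAF rule applied.** Main-period doses fall at V5, V10, V12, V14, V16 and V18 (Protocol Tables 1-1 and 1-2). Suppose the wrong dose is given at V5 only, and take visits in the rule to mean dosing visits (the SAP does not say):

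| Dosing history | Wrong doses | SAF | FAS |
|---|---|---|---|
| All six doses | 1/6 | randomised arm | randomised arm |
| Stops after V5 | 1/1 | moved to other arm | randomised arm |
| Stops after V10 | 1/2 (tie) | excluded | randomised arm |

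The same error has three outcomes, depending only on when dosing stops. An endpoint event can stop it. Under Protocol 6.5 and 7.1.1, an indicated prohibited anticoagulant or antiplatelet interrupts dosing, and an interruption beyond 56 days ends it. Death also ends it.

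**4. Reference effect.** Protocol 2.3 aims at a 25% relative and more than 3-point absolute reduction, so the control risk exceeds 3/0.25 = 12%, over a period that is not stated. Main-period risk is therefore an assumption; take 6% to 12%. The targeted difference is then 0.25 × 6 = 1.5 to 0.25 × 12 = 3.0 points.

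**5. One mis-dosed placebo participant with an event** (counts rounded from these risks):

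- At 12%, 0.12 × 72 = 8.6 placebo and 6.5 active events; use 9 and 6.
  - FAS: 9/72 − 6/72 = 12.50 − 8.33 = 4.17 points.
  - SAF, moved: 8/71 − 7/73 = 11.27 − 9.59 = 1.68 points, a shift of 2.49.
  - SAF, excluded: 8/71 − 6/72 = 11.27 − 8.33 = 2.93 points, a shift of about 1.2.
- At 6%, 0.06 × 72 = 4.3 and 3.2; use 4 and 3.
  - FAS: 4/72 − 3/72 = 5.56 − 4.17 = 1.39 points.
  - SAF, moved: 3/71 − 4/73 = 4.23 − 5.48 = −1.25 points, a shift of 2.64 that reverses the sign.
  - SAF, excluded: 3/71 − 3/72 = 4.23 − 4.17 = 0.06 points, a shift of about 1.3.

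With fixed denominators the shift is 2/72 = 2.78. A moved event therefore shifts the difference between the two arms involved by about 2.5 to 2.8 points.

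**6. Which arms are involved.** A placebo-to-active move needs a wrong vial. A wrong volume from an active vial moves the participant between dose groups. Each of those groups' contrasts with placebo then shifts by roughly half as much; for example, 6/72 to 7/73 is 8.33 to 9.59, or 1.26 points.

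**The case against.** The strongest reply is that this is a permitted choice. Protocol 9.4.1.1 qualifies the FAS default, Protocol 9.4.6 refers details of the exploratory endpoints to the SAP, and the SAP does specify another set. That stands. A reader might infer that the SAP contradicts or breaches the protocol, and the documents do not support this. What remains is that the departure is neither recorded nor explained.

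A second reply is that SAP 6.2.1 does give an aim: efficacy under a constant drug concentration during chronic treatment, matched by the on-treatment label in Table 5-2. This justifies the time window. It does not justify regrouping by dose received, because the FAS can use the same window. The PA scope already ends 28 days after the last dose for those who do not enter the extension.

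Third, FAS/PA and FAS/TA runs of the composite and access thrombosis are planned, and the FAS is dropped only when it equals the SAF. It would be wrong to infer that no as-randomised result will exist. The dispute is over which result leads, and over the subgroup, component and death analyses, for which no FAS run is clearly planned.

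Fourth, the trigger is narrow. Treatment is assigned centrally, vials are numbered, and vial and participant are confirmed at dosing (Protocol 6.3 and 6.4). One error in a full course changes nothing. This stands: the documents report no count of mis-dosed participants, and no bias has been shown. Against it, every dose level is measured by volume from one vial strength (Protocol 6.1), and the sponsor saw reason to add a mis-dosing rule.

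**Conclusion.** The point holds as a minor one. The SAP leads with as-treated grouping for exploratory efficacy, does not record or justify the departure from the protocol default, and uses an assignment rule that can depend on the outcome.

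The effect is zero if nobody is mis-dosed. If a mis-dosed participant has an event and stops dosing near the majority or tie threshold, the shift is about as large as the targeted effect. That comparison rests on the assumed 6% to 12% main-period control risk, a placebo-active swap, and arms of 72. It should not be turned into an annual rate or a fixed share of an arm's events, because Protocol 2.3 gives no time period. Its composite, described for an anticipated pivotal trial, also differs somewhat from the one in SAP 6.2.1.

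Nor do the documents make this comparison decisive for Phase 3. Exploratory efficacy is one part of the snapshot, there is no decision rule, and no hypothesis test is planned for the study in Protocol 9.1. The FAS is itself not an all-randomised set, since it requires one dose.

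**What to change.** In SAP 6.2.1, 6.2.2 and Table 5-2, make FAS with the PA on-treatment data scope the main analysis for both exploratory efficacy endpoints, and SAF the supplementary one. Let the components, death analyses and subgroups follow the main analysis. For overall death this is for consistency within the SAP, since Protocol 9.4.6.1 lists no such endpoint. Align the Table 5-2 footnotes so that the FAS/PA row carries the on-treatment label that its data scope implies. Keep SAF for bleeding and adverse events.

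Log the change and its reason in SAP section 7. SAP 6.5 indicates that the primary analysis was complete before version 4.0, and Protocol 9.4 describes that analysis as unblinded, so the entry should say plainly that the hierarchy was changed after unblinding. It then applies to the final analysis and reporting. If the sponsor prefers to keep SAF as the main set, the minimum is an entry in section 7 that records the departure and justifies grouping by dose received.

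The cost is SAP wording and a few additional FAS tables (components, deaths, subgroups). The FAS/PA and FAS/TA composite runs are already planned, and no sample size changes.
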